2.1 Phase 1: Randomized placebo controlled

Patients will be randomized to receive real or sham rTMS using the variable-sized permuted blocks randomization algorithm (with a maximum block size of 4), with randomization stratified by symptom severity (Y-BOCS total score ≤31 vs. >31) and age $(\le 34 \text{ vs.} > 34 \text{ years at entry})$, to ensure balance in these factors across arms in this small study. Randomizations will be conducted in SAS using procedures outlined by Efird (2011) [Efird, J. Blocked Randomization with Randomly Selected Block Sizes. Int. J. Environ. Res. Public Health., 8, 15-20]. The randomization codes generated by our statistician/data manager for each of the 4 strata will be communicated to the study coordinator at the time of randomization (i.e. at the patient's baseline visit), based on the stratum to which the patient belongs. Patients will be blinded to their treatment arm. Patients will receive 6 weeks of daily treatments Monday through Friday (not on weekends). There will be 3 MRI sessions that will take place (i) within 2 weeks prior to the first TMS session, (ii) at the end of week 1 of treatment and (iii) within 2 weeks after the last TMS session. Longitudinal clinical assessments will take place throughout the course of study at the end weeks 2, 4 and 6 of TMS, in addition to a last assessment 3 months after TMS. Physiological assessments to measure cortical excitability and

plasticity in the motor cortex using single and paired-pulse TMS will also take place the 1st day of treatment and at the end of weeks 2, 4 and 6 of TMS.

Baseline TMS Neurophys TMS Neurophys. TMS Neurophys TMS Neurophys. 8 & 8 8 Clinical Clinical Clinical Clinical Clinical Assessment Assessment Assessment Assessment Assessment 3 mo MRI MRI MRI TMS (6 weeks) Post-TMS

Figure 1: Clinical Trial Design for Phase 1

2.2 Phase 2: Open label TMS

Patients who do not remit following the double-blinded phase of the study will be given the option to enter an open-label phase 2 and receive an additional 6 weeks of real rTMS (regardless of whether they received real or sham TMS in phase 1). Phase 2, like phase 1, will also include an MRI session at the end of week 1 and at the end of week 6, clinical assessment at weeks 2, 4 and 6, and TMS neurophysiological assessments at the end of weeks 2, 4 and 6.

3. Transcranial Magnetic Stimulation

We will use a MagVenture MagPro X100 with MagOption stimulator and two dynamic cooled butterfly coils: one real and one sham (MagVenture, Denmark) navigated with an infrared TMS Neuronavigation Research Premium system (Localite, Germany) to administer the TMS.

We will start by measuring the patient's motor threshold (MT), which is a measure of cortical excitability used to standardize the intensity of stimulation across subjects. To do this, the TMS coil is placed over the hand representation of the primary motor cortex (M1) in a rostro-medial 45° angle. Single pulses are applied with an interpulse interval (IPI) of at least 7 seconds, to prevent additive neuromodulatory effects. When pulses are applied at suprathreshold intensities, a volley of activity travels through the pyramidal motor pathways and leads to the contraction of the contralateral hand muscle. The intensity of stimulation is sequentially reduced until we reach a point when fewer than 50% of the pulses (usually <3 out of 6) lead to a muscle contraction (identified by visual inspection or neurophysiological motor evoked potentials). The first TMS intensity that is unable to elicit a muscle contraction more than 3 out of 6 pulses is considered the motor threshold, and usually expressed as a percentage of the maximum stimulator output.

Once the MT is determined, we will define our target of stimulation using the fMRI data obtained and analyzed days prior to the first TMS session. Using the Localite TMS neuronavigation system we will corregister the patient's head to their MRI, and place the TMS coil over the scalp position that corresponds to the cortical target.

At this point, the treatment session can begin. We will use an inhibitory protocol of 1Hz stimulation at 110% of the motor threshold intensity and a total of 1800 pulses per session. This will have a duration of 30 min. This protocol complies with published safety guidelines (Rossi et al., 2009). Sessions will occur daily Monday through Friday over 6 weeks.

Sham TMS will use the exact same procedure with a sham coil, which is designed to induce the same nonspecific sensory effects of TMS (auditory and somatosensory activation) without inducing the neuromodulatory magnetic fields.

4. Transcranial Magnetic Stimulation neurophysiological measures

The history of TMS has been closely linked to motor neurophysiology; the first applications were indeed geared towards the study of cortical physiology in humans. Both single and paired-pulse protocols have been established to study cortical excitability and plasticity (both intracortical inhibition and facilitation). These protocols lead to robust effects in healthy controls and are used regularly in clinical practice for diagnostic applications in neurological populations (Groppa et al., 2012). Pharmacological studies have been conducted to understand the neurochemical dynamics driving these effects (Paulus et al., 2008). Like all other TMS applications, these measures are noninvasive, and their safety has been well established (Rossi et al., 2009).

OCD results from the deficits in cortical inhibition and excessive excitatory states within specific brain networks. TMS measures of excitability, inhibition and facilitation have been shown to be abnormal in patients with OCD, to reflect clinical severity and to respond to treatment (Mantovani et al., 2013). We will use the following measures to obtain neurophysiological markers of severity and response, in addition to the other neuroimaging and behavioral measures described in this protocol.

The following 5 measures will be assessed:

- Resting Motor Threshold
- Active Motor Threshold
- Cortical Silent Period
- Short-Interval Cortical Inhibition (SICI).
- Intracortical Facilitation (ICF)

4.1 Motor threshold (resting and active)

The resting motor threshold (RMT)/active motor threshold (AMT) are defined as the minimum TMS intensity needed to induce a muscle contraction or motor evoked potential larger than 50 mV in at least 50% of the trials, typically 3 of 6 or 5 of 10 TMS pulses (Groppa et al., 2012). We will reassess the motor threshold following the same procedure used on day 1 of treatment and described above. The resting motor threshold is measured with the muscle of study at rest. The active motor threshold is measured with a voluntary contraction of the muscle. Motor thresholds are measures of cortical excitability and reflect the activity of neuronal membranes and the excitability of corticocortical axons, synapses and their sodium channels (NMDA-associated transmission and GABAergic mechanisms are less involved) (Ziemann, 2004).

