4.3 Short-interval intracortical inhibition (SICI)

The application of a first stimulus below motor threshold followed by a second stimulus above motor threshold, with a short interstimulus interval (ISI) of 1-5 ms, results in a physiological reduction of cortical excitability (short-interval intracortical inhibition (SICI)) (Groppa et al., 2012). This parameter reflects inhibitory effects mediated mainly by GABAA-receptors, as well as dopamine and acetylcholine (Ziemann, 2004).

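### The motor evoked potential cut-off for resting and active motor threshold is printed as 50 mV, apparently in the wrong unit; the effect is limited to thresholds scored by amplitude

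*Combined protocol and SAP*

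**What the plan says.** Section V.4.1 gives a single definition for both resting and active motor threshold: "minimum TMS intensity needed to induce a muscle contraction or motor evoked potential larger than 50 mV in at least 50% of the trials". Contraction and evoked potential are alternatives joined by *or*. No other section gives an amplitude. The same section says of later visits: "We will reassess the motor threshold following the same procedure used on day 1 of treatment and described above". It adds that AMT is taken while the patient voluntarily contracts the muscle.

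The day-1 procedure is in Section V.3. Intensity starts above threshold and is stepped down. Responses are counted over about six pulses, each "identified by visual inspection or neurophysiological motor evoked potentials". The stopping rule is: "The first TMS intensity that is unable to elicit a muscle contraction more than 3 out of 6 pulses is considered the motor threshold". No amplitude appears there.

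The threshold is then used in three places:

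- **Treatment (Section V.3):** "1Hz stimulation at 110% of the motor threshold intensity and a total of 1800 pulses per session".
- **Paired pulses (Sections V.4.3 and V.4.4):** SICI is described as "The application of a first stimulus below motor threshold followed by a second stimulus above motor threshold" at a short interval, and ICF uses the same pairing at longer intervals.
- **Outcomes:** RMT and AMT are two of the five measures listed in Section V.4. Section VI (TMS neurophysiology) compares the course of these measures between arms with a general linear model, at baseline and weeks 2, 4 and 6.

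**The concern.** A threshold criterion is meant to mark a minimal response. The V.4.1 sentence offers contraction and evoked potential as two ways to recognise the same threshold. At 50 mV the two would not agree. Scoring by eye gives one value, while scoring by amplitude gives a much higher value or none.

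Both V.3 and V.4.1 allow scoring by evoked potential. EMG is evidently recorded at these assessments, since Section V.4.2 times the silent period from the evoked potential to the return of EMG activity. Amplitude scoring is therefore a realistic choice, and a member of staff who looks for a cut-off will find only this one.

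AMT is the most exposed measure. The muscle is already contracting when AMT is taken, so a contraction is a poor sign that the pulse had an effect, and the scorer has to lean on the evoked potential.

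At stake is whether RMT and AMT mean the same thing across patients and visits. A change of scoring method would shift the values for reasons unrelated to treatment. That adds noise to the comparison of arms, and it would add bias if the method differed by arm, which the documents give no reason to expect.

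**Working it through.** **1. Is there a figure to reproduce?** No. The 50 mV is a stated criterion and is not derived from other inputs. The check is a unit conversion, a comparison with an assumed range, and a trace of where the criterion is used.

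**2. Conversion.** 50 mV × 1000 = 50,000 microvolts.

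**3. Comparison with possible responses.** The documents give no evoked-potential amplitudes, so the range is an assumption: surface responses of a hand muscle from about 0.05 mV to the low tens of mV. The ratio is 50 divided by the assumed amplitude.

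| Assumed response (mV) | 50 mV ÷ response |
|---|---|
| 0.05 | 1000 |
| 0.5 | 100 |
| 1 | 50 |
| 5 | 10 |
| 10 | 5 |
| 20 (one reading of low tens) | 2.5 |

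Every ratio exceeds 1, so no response in the range passes the cut-off. The conclusion would change only if responses at threshold exceeded 50 mV.

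**4. What each rule returns if responses are scored by that cut-off.**

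- Under V.4.1, threshold is the lowest intensity that succeeds in at least half the trials. If no intensity succeeds, the threshold is unobtainable.
- Under V.3, intensity is stepped down until responses fall short. If none counts, the starting intensity already falls short and would be recorded as the threshold. That overstates it, because the start is meant to be above threshold.
- Under either section, if a response is a muscle contraction, the cut-off plays no part and a threshold is obtained.

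**5. Where the printed figure reaches.**

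| Use | Source of the threshold | Exposed? |
|---|---|---|
| Treatment at 110% | V.3 procedure, no amplitude | Only if staff bring in the V.4.1 cut-off |
| RMT | V.4.1, which refers back to V.3 | If scored by amplitude |
| AMT | V.4.1, during voluntary contraction | If scored by amplitude, which is more likely here |
| SICI, ICF | Pulses set relative to threshold | Only if that threshold was scored by the cut-off |
| Silent period | Timed on EMG | Not through the cut-off |
| Y-BOCS | Clinical rating | No |

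**6. Power and recruitment, as a side check.** Section VI gives 20 per group, two-sided alpha 0.05 and effect size 1.06 for 90% power. The noncentrality is 1.06 × √(20/2) = 3.35 on 38 degrees of freedom, and the power is 0.904, so the statement reproduces. Recruitment is 40 ÷ (1 − 0.30) = 57.1, rounded up to 58 as stated in Section III. Neither figure uses the motor threshold.

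**The case against.** The strongest reply is that the 50 mV sentence is a textbook definition with a citation, and that the working instruction is elsewhere. The next sentence but one refers reassessment back to day 1, and the day-1 procedure counts contractions, allows visual inspection and names no amplitude. On that reading nobody need ever apply 50 mV. In addition, the claim that responses do not reach 50 mV is an assumption, because no section gives a range. A micro sign can also turn into the letter m when a PDF is converted to text. The symbols β, ≤ and ° came through elsewhere, but one ≥ in the inclusion criteria did not, so a conversion fault cannot be ruled out.

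Much of this stands, and it rules out several stronger inferences that a reader might draw:

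- **That the threshold cannot be determined as written.** The contraction branch still gives one.
- **That all treatment sessions in both arms (6 weeks × 5 days = 30 per patient per phase) are wrongly scaled.** The 110% refers to the V.3 threshold, which has no amplitude in it.
- **That staff would keep raising output in search of 50 mV, creating a hazard.** V.3 steps intensity down. The failure it would produce is an overstated threshold, and only if the cut-off is applied there.
- **That four of the five physiological measures are compromised.** SICI and ICF are affected only through a threshold scored by amplitude.
- **That the SICI description contradicts the cut-off.** V.4.3 says only that the first pulse is below threshold. It does not say that this pulse evokes nothing by itself.

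The reply does not dispose of the point. The procedure it relies on itself admits evoked potentials without saying how large one must be. V.3 also does not describe how to find a threshold in a contracting muscle, so AMT is where the V.4.1 definition is most likely to be consulted.

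**Conclusion.** The point holds in limited form. The only evoked-potential cut-off in the plan appears to carry the wrong unit. On the assumed range of 0.05 mV to the low tens of mV, the amplitude branch of the definition would never be met. Thresholds scored by it would be overstated or unobtainable, and not comparable with those scored by eye.

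The effect falls mainly on RMT and especially AMT, two of the five physiological measures. It reaches treatment or paired-pulse intensity only if staff apply the V.4.1 figure when setting them. The documents do not say how many thresholds are scored by amplitude, so the number affected cannot be estimated. The Y-BOCS analysis, the sample size and the power statement are unaffected.

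The conclusion rests on the assumed amplitude range and on the source file also reading mV. It is an error worth correcting in the study procedures and does not threaten the primary result.

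**What to change.** 1. Read the unit in V.4.1 from the source file and check it against the practical guide cited in that sentence. Correct it if it is misprinted.
2. Reconcile V.3 with V.4.1 so that both use one stated response criterion, including what counts as a response when evoked potentials are scored and when the muscle is already contracting. The investigators must settle that criterion; no clinical value is proposed here.
3. The same edit should reconcile the counting rules, which is a separate matter: V.3 takes the first intensity that falls short, whereas V.4.1 takes the lowest that succeeds.

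The unit correction is a one-line amendment, and the reconciliation adds a sentence or two. No extra procedure, visit or patient is needed.

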4.2 Cortical silent period

The cortical silent period CSP is defined as a reduction of the ongoing tonic muscle activity, lasting up to 300 ms after the contralateral TMS pulse to the primary motor cortex. It can be subdivided into the contralateral (CSP) and the ipsilateral (ISP) cortical silent period. Its length can be defined as the duration from the beginning of an MEP to

the re-emergence of baseline EMG-activity. The first 50 ms represent spinal mechanisms of inhibition, while later inhibition is influenced by cortical networks (Chen et al., 1999). This inhibitory phenomenon is thought to be driven primarily by GABAB-receptors (Ziemann, 2004). The ISP represents neuronal activity on the muscle ipsilateral to the site of stimulation and, therefore, measures cortical phenomena contralateral to the site of stimulation and the function of the corpus callosum connecting both hemispheres (Meyer et al., 1995).

4.3 Short-interval intracortical inhibition (SICI)

The application of a first stimulus below motor threshold followed by a second stimulus above motor threshold, with a short interstimulus interval (ISI) of 1-5 ms, results in a physiological reduction of cortical excitability (short-interval intracortical inhibition (SICI)) (Groppa et al., 2012). This parameter reflects inhibitory effects mediated mainly by GABAA-receptors, as well as dopamine and acetylcholine (Ziemann, 2004).

4.4 Intracortical facilitation (ICF)

The same paired-pulse configuration used in SICI but applied at longer ISIs of 10-17 ms or longer results in increased excitability (Groppa et al., 2012). This intracortical facilitation (ICF) seems to be mediated principally by glutamatergic neurotransmission, although the underlying physiology is less clear in this case (Ziemann, 2004).

5. Magnetic Resonance Imaging

MRI sessions will include both structural and functional imaging. MRI scanning will be conducted on a 3T scanner equipped with multichannel receivers. Protocols have been developed and validated at the Martinos Center for Biomedical Imaging. Resting state MRI sessions will be obtained while participants focus on a fixation cross (functional scans) or have their eyes closed (structural scans). Task fMRI scans (see fear conditioning below) will be performed while subjects have their eyes open and receive visual, auditory and somatosensory stimulation via integrated MRI-compatible audiovisual equipment. Patient will be required to respond using an MRI-compatible fiber-optic response-box.

5.1 Multi-Source Interference Task

The Multi-Source Interference Task (MSIT) is a cognitive paradigm that was designed to reliably identify the cingulo-frontal-parietal cognitive/attention network (CFP network) within individual subjects (Bush et al., 2006). Among other relevant brain regions, the pre-SMA and dorsal anterior cingulate cortex are activated in this 10-15 task when performed inside of the scanner. We will use this fMRI cognitive paradigm to identify our target of stimulation on an individual-subject basis.

Briefly, the MSIT presents a string of 3 numbers to subjects, which can be different combinations of 0,1,2,3 in which 2 numbers are the same and one is different (e.g. 100, 323, 221). Subjects are asked to identify what number is different by pressing one of 3 buttons available in the response box. Some trials will be congruent (e.g. 100) and some incongruent (010), depending on the position of the number that is different. Analyzing the brain response to these congruent and incongruent trials has been shown to robustly

identify these brain networks and regions at the individual level in healthy and patient populations (Bush et al., 2006).

5.2 Fear Conditioning:

All subjects randomized prior to February 27th, 2018 will undergo a 2-day fear conditioning protocol. The experiments will be carried out in a 3T scanner. In accordance with previously published procedures (Orr et al., 2000), prior to the initiation of the experiment, recording electrodes will be attached to the palm of the subject's non-dominant hand to measure SCR, and stimulating electrodes will be connected to two fingers of the subject's dominant hand through which the electric shock will be delivered. SCR will be measured through 9-mm (sensor diameter) Sensor Medics Ag/AgCl electrodes (safe for use in the magnet environment).

Subjects will view two rooms presented on a monitor, both of which differ in color and content (e.g., an office and a kitchen). The conditioned stimuli (CSs) will be different cues in the room. The CS+ and the US will only be presented in one context (conditioning context; CX+). The other context will be used for extinction training (CX-). Neither CS+ presented in the context of the CX-, nor a CS- presented in either context, will ever be paired with the US. In one of the four possible CS-CX combinations, for example, the office will serve as the dangerous context, in which the subjects will receive electric currents only when the yellow light is on, whereas the kitchen will serve as the safe context, in which no electric currents will be delivered. On day 2, subjects are placed back in the magnet and will be presented with additional extinction trials to CSs in pseudorandomorder.

As of February 27th, 2018, the fear conditioning paradigm will no longer be administered to participants in this study. All fear conditioning data collected prior to February 27th will be analyzed.

VI. BIOSTATISTICAL ANALYSIS

Analysis of Aim 1: To compare change in OCD symptom severity by treatment group, we will utilize a mixed effects linear regression model with Y-BOCS total score as the outcome, a random effect for time (study week), a fixed effect for group (rTMS versus placebo stimulation), and the interaction between time and treatment group (which is the covariate of interest). We will also control for potential confounding by any covariates that are significantly imbalanced between the treatment groups.

Analysis of Aim 2.1: Specification of the analyses examining whether decreased connectivity between the pre-SMA, the Orbito-Frontal Cortex (OFC) and dorsal Anterior Cingulate Cortex (dACC) correlates with clinical improvement can be found below, in the MRI data section - Resting state Connectivity Analysis.

Analysis of Aim 2.2: Specification of the analyses examining whether TMS improves fear extinction retention from pre- to post-treatment, and whether increased functional activation of the fear extinction network (vmPFC, dACC, and hippocampus) during extinction recall can be found below, in the MRI data section - Fear Extinction.

Analysis of Aim 3: To identify biomarkers and predictors of treatment response, we will us linear regression analysis to examine predictors of clinical improvement. The outcome will be the post-treatment Y-BOCS score, the covariate of interest will be each ROI (examined in separate models to begin with, to avoid issues of collinearity), and we will control for the pre-treatment Y-BOCS score. Univariately significant predictors will then be entered into a multivariate linear regression model using step-wise selection (alpha=0.10 to enter, alpha=0.05 to stay).

TMS neurophysiology

Numeric values for each of our 5 physiological measures will be obtained at each of the established times (baseline, week 2, week 4, week 6). A general linear model will be used to assess the difference in longitudinal progression of these measures between the active and placebo group.

MRI data

Fear Extinction

During the extinction training on day 1, the principal contrast for the fMRI data will be CS+ vs. CS-, to establish the substrates of extinction learning. During extinction recall on day 2, the principal contrast will be CS+1 vs. CS+2. Analyses of SCR will test for group x condition interactions for OCD vs. HC with respect to CS2 vs. CS1. With respect to the fMRI data, the initial analysis will involve assessing for a main effect of condition (across both groups), by comparing CS1 vs. CS2 during extinction learning and recall. Finally, voxel-wise analyses will also be performed to identify specific loci of significant group x condition interactions (OCD, HC x CS2, CS1) within designated prefrontal search territories of interest.

With respect to SCR analyses, the SCR for each CS will be calculated by subtracting the mean level for the 2 s immediately preceding CS onset from the highest value among those recorded during the 10-s CS interval. Values will be subjected to repeated measures ANOVA to test hypotheses regarding both within-group and between-group differences at an alpha of p<0.05. Significant interactions will be followed-up with t-tests where indicated. Change in clinical symptoms from pre- to post-treatment, such as the change in YBOCS scores will be correlated with improved extinction retention index from pre- to post-treatment. Voxel-wise regression using change in YBOCS scores will be conducted against BOLD responses during extinction learning and recall to identify changes in functional activation of brain regions associated with change in clinical symptoms.

Multi-Source Interference Task

Standard task-based neuroimaging analyses procedures will be used to analyze the brain activity resulting from patients performing the MSIT in the scanner, including preprocessing and statistical parametric mapping using general linear models.

Resting state Connectivity Analysis

Functional connectivity analysis will employ a regional approach based on Biswal (Biswal, Yetkin, Haughton, & Hyde, 1995) and extended in Fox (Fox et al., 2005) and Vincent (Vincent et al., 2006). This approach has been previously used by our group and

others to study the medial temporal lobe memory system (Kahn, Andrews-Hanna, Vincent, Snyder, & Buckner, 2008), the frontal parietal control system involved in executive function (Vincent et al., 2006), and the default network (Buckner & Vincent, 2007), as well as initial explorations in aging (Andrews-Hanna et al., 2007). Following standard preprocessing, several additional steps are employed to condition the fMRI data for analysis of voxel-based correlations (described in Vincent 2006). Temporal band-pass filtering will remove frequencies greater than 0.08Hz. Several sources of spurious variance along with their temporal derivatives will then removed from the data through linear regression: (i) six parameters obtained by rigid body correction of head motion, (ii) the whole-brain signal averaged over a fixed region in atlas space, and (iii) the signal from a ventricular region of interest and a region centered in the white matter. In this manner, variance unlikely to be involved in spatially specific regional correlations is removed from the data. The global (whole brain) signal may correlate with respirationinduced fMRI signal fluctuations or result from global fluctuations in neuronal activity. Removing signals correlated with ventricles and white matter is an additional means of reducing non-neuronal contributions to BOLD correlations (Fox et al., 2005). Following preparation, maps of functional connectivity are obtained by plotting the correlation strength at each voxel to the time course of a seed region. Between-region correlations are obtained by extracting the time courses for multiple regions and computing the correlation coefficient between regions pairs. ANCOVA analysis will be performed covarying for the clinical and behavioral measures.

Cortical reconstruction and volumetric analysis

Cortical reconstruction and volumetric segmentation will be performed with the Freesurfer image analysis suite, which is documented and freely available for download online (http://surfer.nmr.mgh.harvard.edu/). The technical details of these procedures are described in prior publications (Dale et al., 1999; Dale and Sereno, 1993; Fischl and Dale, 2000; Fischl et al., 2001; Fischl et al., 2002; Fischl et al., 2004a; Fischl et al., 1999a; Fischl et al., 1999b; Fischl et al., 2004b; Han et al., 2006; Jovicich et al., 2006; Segonne et al., 2004)). Briefly, this processing includes motion correction and averaging (Reuter et al. 2010) of multiple volumetric T1 weighted images (when more than one is available), removal of non-brain tissue using a hybrid watershed/surface deformation procedure (Segonne et al., 2004), automated Talairach transformation, segmentation of the subcortical white matter and deep gray matter volumetric structures (including hippocampus, amygdala, caudate, putamen, ventricles)(Fischl et al., 2002; Fischl et al., 2004a) intensity normalization (Sled et al., 1998), tessellation of the gray matter white matter boundary, automated topology correction (Fischl et al., 2001; Segonne et al., 2007), and surface deformation following intensity gradients to optimally place the gray/white and gray/cerebrospinal fluid borders at the location where the greatest shift in intensity defines the transition to the other tissue class (Dale et al., 1999; Dale and Sereno, 1993; Fischl and Dale, 2000). Once the cortical models are complete, a number of deformable procedures can be performed for further data processing and analysis including surface inflation (Fischl et al., 1999a), registration to a spherical atlas which utilized individual cortical folding patterns to match cortical geometry across subjects (Fischl et al., 1999b), parcellation of the cerebral cortex into units based on gyral and sulcal structure (Desikan et al., 2006; Fischl et al., 2004b), and creation of a variety of

surface based data including maps of curvature and sulcal depth. This method uses both intensity and continuity information from the entire three dimensional MR volume in segmentation and deformation procedures to produce representations of cortical thickness, calculated as the closest distance from the gray/white boundary to the gray/CSF boundary at each vertex on the tessellated surface (Fischl and Dale, 2000). The maps are created using spatial intensity gradients across tissue classes and are therefore not simply reliant on absolute signal intensity. The maps produced are not restricted to the voxel resolution of the original data thus are capable of detecting submillimeter differences between groups. Procedures for the measurement of cortical thickness have been validated against histological analysis (Rosas et al., 2002) and manual measurements (Kuperberg et al., 2003; Salat et al., 2004). Freesurfer morphometric procedures have been demonstrated to show good test-retest reliability across scanner manufacturers and across field strengths (Han et al., 2006; Reuter et al., 2012).

To extract reliable volume and thickness estimates, images will be automatically processed with the longitudinal stream in FreeSurfer (Reuter et al., 2012). Specifically an unbiased within-subject template space and image (Reuter and Fischl, 2011) is created using robust, inverse consistent registration (Reuter et al., 2010). Several processing steps, such as skull stripping, Talairach transforms, atlas registration as well as spherical surface maps and parcellations are then initialized with common information from the within-subject template, significantly increasing reliability and statistical power (Reuter et al., 2012).

Diffusion MRI and Tractography

Diffusion images will be corrected for motion and eddy currents, using affine registration to a b0 reference volume, by using FSL-based software. A tensor model will then be fitted to each voxel, generating different diffusivity maps. Finally, we will use TBSS (Smith et al., 2006) to perform voxel-wise statistical analyses for relevant diffusivity measures: functional anisotropy (FA), and mean axial and radial diffusivity (MD, AD, RD).

Two-tensor whole brain tractography will be implemented for tract analysis. This form of tractography involves a recursive process that both fits local parameters at each step and propagates the fiber in the most stable direction, allowing simultaneous tractography and model estimation. This model also uses a covariance matrix to measure confidence, which reduces false positives, and implements two eigenvalues per voxel, which improves resolution of and accounts for branching and crossing fibers. Whole-brain tractography will be used to best account for all potential tracts among the ROIs, which may be otherwise limited in solely ROI-based tractography (Yang et al., 2014).

Power for the Primary Aim

For the primary analysis comparing change in Y-BOCS total score by treatment group, with 20 patients per group and a two-sided alpha of 0.05, we will have 90% power to detect an effect size of 1.06. Due to the novelty of our approach, no comparable data exist to inform the power calculation. However, Mantovani et al. (2010) examined change in Y-BOCS total score among 18 OCD patients (completers) randomized to 4 weeks of similar rTMS or sham treatment. Based on their reported F-statistic comparing change in Y-BOCS total score after 4 weeks of treatment, their observed effect size,

expressed as Cohen's d (Thalheimer & Cook, 2002), was 1.8. Based on these results, we believe that our study will be adequately powered to detect anticipated effect sizes.

VII. RISKS AND DISCOMFORTS

Participation in this study poses minimal foreseeable risks. Patients may experience psychological discomfort when discussing psychiatric history and/or current psychiatric symptoms or side effects. Answering detailed questionnaires may also create some inconvenience for subjects. Confidentiality of all subjects will be protected per institutional and federal requirements.

Repetitive TMS at high frequencies has the rare potential to induce a seizure even in healthy individuals (~ 8 reported cases worldwide since the invention of TMS in 1985), but the risk for seizure can be effectively managed by using appropriate subject selection criteria and by keeping the TMS parameters within the safety parameters of the international safety consensus (Rossi et al., 2009). In addition, this study proposes the use of low-frequency rTMS, which has a cortical inhibitory effect, and single-pulse TMS for physiological assessments, which does not have carry-over cumulative effects. To protect subjects from the risk of a seizure, this study strictly adheres to the international safety consensus and will exclude subjects at increased risk for seizures (Rossi et al., 2009). In the unlikely event that a suspected seizure would occur, the seizure stops as soon as TMS is stopped, and the TMS clinical service safety plan is activated, including transfer of the subject with ambulance to MGH ER for a medical and neurological evaluation. No one has ever developed epilepsy as a consequence of TMS. There are no known or foreseeable long-term risks associated with TMS. TMS is not uncomfortable but the subject may feel twitching of the scalp muscles during stimulation. It is possible that the subject may feel headache after the TMS measurement that is caused by keeping the head in the same position for a lengthy period of time and/or by stimulation of the scalp muscles and nerves by the TMS pulses. The headache, if present, is typically mild, disappears soon and, if needed, can be treated by mild over-the-counter analgesics that are available to study participants.

The risks of the MRI examination are essentially identical to those of a standard, clinically employed, anatomical MRI study. There is no ionizing radiation. The technique is non-invasive and we will not administer any contrast agent. A certain percentage of people cannot tolerate the MRI environment, usually due to claustrophobia. We will monitor subjects and we will be in constant auditory contact with the subjects. The study can be immediately stopped at the subject's request. The MR machine will make a number of sounds; the intensity of these sounds is not harmful to one's hearing if one wears a headphone or earplugs which will be routinely provided to our subjects. Contraindications to participating in MRI studies exist for those subjects who have metallic or other electronic devices implanted such as pacemakers, electronic implants, shrapnel in the eye, certain intracranial aneurysm clips, etc. All subjects will fill out a detailed questionnaire with regard to any implanted metal or devices or any shrapnel injuries. These contraindications constitute reasons for exclusion from the present study.

The safety of our fear conditioning paradigm has been established and approved in multiple IRB-approved research protocols world-wide and at MGH. The electrical shock that will be applied to the fingers during the fear conditioning paradigm is uncomfortable but not painful. The finger stimulator is powered by a 9V battery and has been approved by Partners Biomedical Engineers.

